7.3.5 Baseline Examinations

Subjects with abnormal baseline physical exam results will be tabulated by examination criteria (e.g., neck, cardiovascular, lungs, etc.) and for all treated subjects, according to the general methods.

7.4 Extent of Exposure

7.4.1 Administration of Study Therapy

The following parameters will be summarized (descriptive statistics) for all treated subjects, according to the general methods:

- Number of combined doses received (nivolumab + ipilimumab). A subject will be considered to have received combined doses of ipilimumab and nivolumab, if both infusions are administered on the same date.
- Number of doses received (nivolumab by treatment period, ipilimumab)
- Cumulative dose (nivolumab by treatment period, ipilimumab) in mg/kg
- Relative dose intensity (%) using the following categories: < 50%; 50 - < 70%; 70 - < 90%; 90 - < 110%; ≥ 110%. (nivolumab by treatment period, ipilimumab)
- Treatment duration (nivolumab by treatment period, ipilimumab) in weeks.

Table 7.4.1-1: Study Therapy Parameter Definitions

	Nivolumab in period 1	Nivolumab in period 2	Ipilimumab in period 1
Dosing Schedule per Protocol	1 mg/kg every 3 weeks for 4 doses	3 mg/kg or 240 mg flat dose every 2 weeks	3 mg/kg every 3 weeks for 4 doses
Actual Dose (mg)	Actual Dose (mg) is defined as the total dose delivered (mg)	Actual Dose (mg) is defined as the total dose delivered (mg)	Actual Dose (mg) is defined as the total dose delivered (mg)
Actual Dose Level (mg/kg)	Actual Dose Level (mg/kg) is defined as the total dose delivered (mg) /most recent weight (kg)	Actual Dose Level (mg/kg) is defined as the total dose delivered (mg) /most recent weight (kg)	Actual Dose Level (mg/kg) is defined as the total dose delivered (mg) /most recent weight (kg)
Cumulative Dose (mg/Kg)	Cumulative Dose (mg/kg) is the sum of the actual dose levels administered to a subject.		Cumulative Dose (mg/kg) is the sum of the actual dose levels administered to a subject.
Relative Dose Intensity (%)	Cumulative dose(mg/kg)/ [1 x (Last dose date – Start dose date + 21)/21] x 100		Cumulative dose(mg/kg) /[3 x (Last dose date - Start dose date + 21)/21] x 100

Table 7.4.1-1: Study Therapy Parameter Definitions

	Nivolumab in period 1	Nivolumab in period 2	Ipilimumab in period 1
Duration of Treatment	Last dose date - Start dose date +1 in period 1	Last dose date - Start dose date +1 in period 2	Last dose date - Start dose date +1 in period 1

*. For post-progression exposure, only doses administrated after progression will be included to derive these parameters.

Duration of treatment will also be presented using a Kaplan-Meier curve whereby the last dose date will be the event date for those subjects who are off study therapy. Median duration of treatment and associated 95% CI will be provided. Subjects who are still on study therapy will be censored on their last dose date.

A by-subject listing of dosing of study medication (record of study medication, infusion details, and dose changes) and a listing of batch numbers will be also provided.

7.4.2 Modifications of Study Therapy

7.4.2.1 Dose Delays

Either nivolumab or ipilimumab infusion may be delayed. A dose will be considered as actually delayed if the delay is exceeding 3 days (i.e. greater than or equal to 4 days from scheduled dosing date) for both nivolumab and ipilimumab. All study drugs must be delayed until treatment can resume. Reason for dose delay will be retrieved from CRF dosing pages.

The number of dose delays per subject, length of delay, and reason for delay will be summarized for all subjects, according to the general methods.

7.4.2.2 Infusion Interruptions and Rate Changes

Each nivolumab or ipilimumab infusion can be interrupted and/or the IV infusion rate can be reduced. This information will be retrieved from CRF dosing pages.

The following parameters will be summarized for all treated subjects, according to the general methods:

- Number of subjects with at least one dose infusion interruption, the reason for interruption, and the number of infusion interruptions per subject.
- Number of subjects with at least one IV infusion rate reduction and the reason for reduction.

7.4.2.3 Dose Escalations

Dose escalations are not permitted for either nivolumab or ipilimumab.

7.4.2.4 Dose Reductions

Dose reductions are not permitted for either nivolumab or ipilimumab.

7.4.2.5 Dose Omissions

Dose omissions are not permitted for either nivolumab or ipilimumab.

7.4.3 Concomitant Medications

Concomitant medications, defined as medications other than study medications which are taken at any time on-treatment (i.e., on or after the first day of study therapy and within 100 days following the last dose of study therapy), will be coded using the WHO Drug Dictionary.

Concomitant medications will be listed for all treated subjects. Concomitant medications will also be summarized (subjects with any concomitant medication, subjects by medication class and generic term) for all treated subjects, according to the general methods.

7.5 Efficacy

7.5.1 Secondary Analyses

7.5.2 Survival

Overall Survival (OS) and Progression-Free Survival (PFS) will each be summarized using the Kaplan-Meier method. Median values of OS and PFS, along with two-sided 95% confidence intervals using the Brookmeyer and Crowley method will be calculated and presented. Corresponding Kaplan-Meier curves will be produced for OS and PFS based on all treated subjects and subgroups defined in Section 6.4.

7.5.3 Objective Response Rate

The investigator-assessed Objective Response Rate (ORR) will be summarized by binomial response rates and their corresponding two-sided 95% exact confidence intervals using the Clopper-Pearson method. BOR will be tabulated. ORR and BOR will be analyzed for all treated subject as well as subgroups defined in Section 6.4.

7.5.4 Duration of Objective Response

The DOR will be summarized using the Kaplan-Meier method for subjects who achieve a PR or CR. Median values of DOR, along with two-sided 95% confidence intervals using the Brookmeyer and Crowley method, will also be calculated. This analysis will be performed for subjects achieving PR/CR among all treated subjects.

7.6 Safety

7.6.1 Primary Analyses

7.6.1.1 High Grade Treatment-Related Select Adverse Events of Potentially Immune-Mediated Etiology

The number and percentage of subjects who report high-grade (Grade 3-5), treatment-related, select adverse events of potentially immune-mediated etiology (pulmonary, gastrointestinal, skin, renal, hepatic, endocrine, infusion related or hypersensitivity) will be summarized for all treated subjects overall and subgroups. High grade (Grade 3-5) treatment-related select adverse events will be tabulated using worst grade per CTCAE v4.0 criteria by system organ class and Medical Dictionary for Regulatory Affairs (MedDRA) preferred term.

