- ^b In case of an on-hold period during therapy, subjects may be treated for more than 24 months but for a maximum of 50 cycles.
- ^c Subjects may be treated beyond progression under protocol-defined circumstances.

The start of the trial is defined as the first patient’s first study visit. End of trial is defined as the last patient’s last study visit. Study completion is defined as the final date on which data for the primary endpoint was or is expected to be collected, if this is not the same.

Enrollment of new subjects into the study will stop at the time of marketing authorization approval. In certain countries where nivolumab plus ipilimumab combination regimen may not be immediately available upon marketing authorization and subject to country specific amendments, enrollment may remain open for a maximum of 1 year after marketing authorization is granted.

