8 STATISTICAL CONSIDERATIONS

8.1 Sample Size Determination

Of 768 subjects who will be screened to receive first-line therapy for advanced disease with histologically confirmed stage III (unresectable) or stage IV melanoma, approximately 615 subjects will be treated with nivolumab and ipilimumab regimen. This sample size is based on the primary objective of the study: determining the incidence of high-grade (CTCAE v4.0 Grades 3-5), treatment-related, select adverse events of potentially immune-mediated etiology in subjects receiving first-line therapy for advanced disease. The sample size will allow for estimating an incidence of about 50% with a 95% CI of (46.06%, 54.11%) under 308 subjects with events among 615 treated subjects.

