8.4.3 Safety Analyses

8.4.3.1 Primary Analyses

The number and percentage of subjects who report high-grade (Grade 3-5), treatment-related, select adverse events of potentially immune-mediated etiology will be summarized for all treated subjects overall. High-grade (Grade 3-5), treatment-related select adverse events will be tabulated using worst grade per CTCAE v4.0 criteria by system organ class and Medical Dictionary for Regulatory Affairs (MedDRA) preferred term.

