5 SAMPLE SIZE AND POWER

Of 768 subjects who will be screened to receive first-line therapy for advanced disease with histologically confirmed stage III (unresectable) or stage IV melanoma, approximately 615 subjects will be treated with nivolumab and ipilimumab regimen. This sample size is based on the primary objective of the study: determining the incidence of high-grade (CTCAE v4.0 Grades 3-5), treatment-related, select adverse events of potentially immune-mediated etiology in subjects receiving first-line therapy for advanced disease. The sample size will allow for estimating an incidence of about 50% with a 95% CI of (46.06%, 54.11%) under 308 subjects with events among 615 treated subjects.

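### Does the primary incidence need a stated confidence interval because enrollment may close before 615 subjects are treated?

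*SAP*

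**What the plan says.** **Basis for the sample size.** Protocol 8.1 plans about 615 treated subjects out of 768 screened and gives one reason: "This sample size is based on the primary objective of the study". SAP 5 repeats the text, including "The sample size will allow for estimating an incidence of about 50% with a 95% CI of (46.06%, 54.11"%), and both documents attach the condition of 308 subjects with events among 615 treated. No hypothesis, power or minimum precision is given.

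**End of enrollment.** Protocol 3.1 says: "Enrollment of new subjects into the study will stop at the time of marketing authorization approval". In certain countries, subject to country-specific amendments, enrollment may stay open for up to 1 year longer. SAP 2.1 and SAP 5 do not mention this rule.

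**Primary analysis.** SAP 7.6.1.1 plans "The number and percentage of subjects who report high-grade (Grade 3-5), treatment-related, select adverse events of potentially immune-mediated etiology", for all treated subjects and by subgroup. Under Protocol 8.4.3.1 the same count and percentage "will be summarized for all treated subjects overall". Neither section names an interval.

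**Other analyses.** The response rate is "summarized by binomial response rates and their corresponding two-sided 95% exact confidence intervals using the Clopper-Pearson method" (SAP 7.5.3). SAP 7.5.2 plans "Median values of OS and PFS, along with two-sided 95% confidence intervals", and SAP 7.5.4 does the same for duration of response. SAP 7.4.1 adds: "Median duration of treatment and associated 95% CI will be provided".

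**What lies elsewhere.** SAP 7.1 sends general methods for the safety analyses, adverse events included, to the CA209 Core Safety SAP version 5. SAP 9.1 leaves table detail to a Data Presentation Plan. Neither document was available.

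**The concern.** Where a trial tests nothing and estimates one incidence, precision is the whole case for its size. Here the quantity that sized the study has no stated interval in its own analysis section, while secondary estimates and even treatment duration do. The enrollment rule seems to make this worse. If authorization comes before 615 subjects are treated, the only interval in the documents for the primary incidence is one calculated for a larger study. A reader might take it as the precision achieved, and nothing visible in the analysis text would correct that. At stake would be an overstated precision for the main safety result.

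**Working it through.** **Inputs.** x = 308 events, n = 615 treated, 95% level (Protocol 8.1, SAP 5). The number treated when enrollment closes is not in the documents, so smaller values of n are assumptions.

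**Formula.** Exact (Clopper-Pearson) two-sided 95% limits:

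- lower = 0.025 quantile of Beta(x, n − x + 1)
- upper = 0.975 quantile of Beta(x + 1, n − x)

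**Step 1: reproduce the planned figure.** With x = 308 and n = 615 the point estimate is 308/615 = 50.08%.

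| Method | Lower | Upper |
|---|---|---|
| Clopper-Pearson | 46.06% | 54.11% |
| Wald | 46.13% | 54.03% |
| Wilson | 46.14% | 54.02% |
| Wald, continuity-corrected | 46.05% | 54.11% |

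Only Clopper-Pearson matches both stated limits. The planning figure is correct, with width 54.11 − 46.06 = 8.05 points.

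**Step 2: does the interval depend on n alone?** No. Keep n = 615 and change the count:

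- 246 events (40%): 36.10% to 43.99%, width 7.89 points
- 184 events (30%): 26.32% to 33.71%, width 7.39 points

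Full enrollment would therefore not reproduce the stated limits unless the incidence also came out near 50%. The planning interval illustrates precision close to the widest case. It was never going to be the interval of the result.

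**Step 3: how much precision would a shortfall cost?** Exact intervals at 50% incidence (308/615 in the first row):

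| Treated (assumed below 615) | 95% CI | Half-width, points |
|---|---|---|
| 615 | 46.06% to 54.11% | 4.0 |
| 550 | 45.74% to 54.26% | 4.3 |
| 500 | 45.53% to 54.47% | 4.5 |
| 400 | 44.99% to 55.01% | 5.0 |
| 300 | 44.20% to 55.80% | 5.8 |
| 200 | 42.87% to 57.13% | 7.1 |

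Half-width grows roughly as 1/√n. As a check at 400: 4.02 × √(615/400) = 4.02 × 1.24 = 4.98, against 5.01 exact. Losing about a third of the subjects (615 to 400) costs 1 point of half-width.

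**Step 4: does leaving the method unnamed open a choice that matters?** The largest difference in either limit between the exact interval and Wald or Wilson is 0.086 point at 308/615 and 0.178 point at 150/300. Any standard choice gives essentially the same interval.

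**Step 5: is the information for the interval already planned?** Yes. SAP 7.6.1.1 gives the count and percentage among all treated subjects, and SAP 7.3.1 reports the numbers enrolled and treated. SAP 7.2.1 summarizes accrual of treated subjects by month, site and country. A shortfall would be visible, and x and n determine the exact interval.

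**Step 6: are the two parts of the concern connected?** Only loosely. An interval that is not stated is equally unstated at n = 615. The enrollment rule means only that 615 is not assured; it does not create the omission.

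**The case for a change.** The best case for a change is that it would cost almost nothing. One sentence in SAP 7.6.1.1 could give the overall incidence an exact interval by the method that reproduces the planning figure and already serves the response rate. Naming the method and level for the primary estimate is a normal job for an SAP. The answer that the Core Safety SAP may cover it is not complete either: SAP 7.6.2.2, 7.6.2.3 and 7.6.3 each cite that document, and 7.6.1.1 does not.

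The observation stands: the visible primary-analysis text names no interval. Its weight is small. The general pointer in SAP 7.1 covers safety analyses as a whole, so the absence of a rule cannot be established from the two documents at hand. The contrast with response rate, survival and duration of response is weaker than it looks, because those are efficacy analyses, and the methods that SAP 7.1 hands to the Core Safety SAP are safety methods. Treatment duration in SAP 7.4.1 is the one non-efficacy example.

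The charge that the planning interval overstates the precision of the result does not stand. Both documents state the interval's condition beside it and call 615 approximate, and no section offers it as the interval for the data. Adding achieved precision to SAP 5 would place a result in a planning section and change no analysis.

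**Conclusion.** No change is needed. This is a reporting detail that the analyst can fill from the planned count and denominator. The plan as written gives a well-defined incidence among all treated subjects, and closing enrollment on an outside event does not by itself bias that estimate.

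The size is modest even if a shortfall is assumed: half-width at 50% incidence rises from 4.0 points at 615 to 5.0 at 400, and only a loss of about half the subjects or more brings it to 5.8 (300) or 7.1 (200). The documents give no authorization date, accrual rate or number treated, so no shortfall can be asserted. The choice among exact, Wald and Wilson moves a limit by less than 0.2 point at 308/615 and 150/300. No hypothesis, threshold or decision rule uses the width.

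The conclusion assumes that the report shows the count and the number treated, as SAP 7.6.1.1 and 7.3.1 plan. It does not depend on what the Core Safety SAP says. Naming an exact interval in SAP 7.6.1.1 would be harmless tidying, but the result would be the same.

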7.6.2 Secondary Analyses

7.6.2.1 High Grade Treatment-Related Select Adverse Events of Potentially Immune-Mediated Etiology in Relevant Subgroups

The number and percentage of subjects who report high grade (Grade 3-5), treatment-related, select adverse events of potentially immune-mediated etiology will be summarized overall and for each subgroup defined in Section 6.4. All high-grade (Grade 3-5), treatment-related, select adverse events will also be tabulated according to the general methods.

7.6.2.2 Select Adverse Events of Potentially Immune-Mediated Etiology

Select adverse events of potentially immune-mediated etiology will be summarized according to their incidence, as well as their time to onset and resolution as described in Section 7.6.6 of the CA209 Core Safety SAP version 5. High grade (Grade 3-5) select adverse events of potentially immune-mediated etiology will also be summarized overall and for each subgroup of interest.

7.6.2.3 Immune-Modulating Medications

Immune-modulating medications received by subjects for the treatment of adverse events will be summarized according to Section 7.6.7 of the CA209 Core Safety SAP version 5 according to the general methods. Immune-modulating medications are defined by a series of search terms according to ATC codes, generic codes, and generic names of medications from the BMS medication coding dictionary that is defined and maintained by BMS in a separate file.

7.6.3 Other Safety Analyses

Other safety analyses will be conducted as below as specified in the CA209 Core Safety SAP version 5.

- 1) Deaths
- 2) Serious Adverse Events
- 3) Adverse Events Leading to Discontinuation of Study Therapy
- 4) Adverse Events Leading to Dose Modification
- 5) Adverse Events
- 6) Multiple Adverse Events

- 7) Laboratory Parameters
- 8) Vital Signs and Pulse Oximetry
- 9) Pregnancy
- 10) Adverse Events by Demographic Subgroups

7.6.4 Adverse Events by Standardized MedDRA Query (SMQ)

Adverse events will be searched against SMQ and mapped to SMQ term and scope (broad, narrow), only anaphylactic reaction (SMQ) events will be analyzed in this study. AEs and drug-related AEs that started within 48 hours of infusion will be summarized by SMQ/preferred term and by SMQ scope (broad, narrow), respectively. Additional tables will be created as follows for anaphylactic reaction (SMQ) events:

- Total number and exposure adjusted events by SOC/preferred term and SMQ scope (broad or narrow) within 48 hours of infusion,
- Total number and exposure adjusted drug-related events by SOC/preferred term and SMQ scope (broad or narrow) within 48 hours of infusion.

[REDACTED]

[REDACTED]

[REDACTED]

[REDACTED]

[REDACTED]

- [REDACTED]
- [REDACTED]
- [REDACTED]
- [REDACTED]

[REDACTED]

[REDACTED]

- [REDACTED]
- [REDACTED]
- [REDACTED]
- [REDACTED]
- [REDACTED]
- [REDACTED]
- [REDACTED]
- [REDACTED]
- [REDACTED]
- [REDACTED]

[REDACTED]

[REDACTED]

[REDACTED]

[REDACTED]

[REDACTED]

[REDACTED]

[REDACTED]

[REDACTED]

[REDACTED]

8 CONVENTIONS

Conventions are described in Section 8 of the CA209 Core Safety SAP version 5.

9 CONTENT OF REPORTS

9.1 Clinical Study Report

Statistical components for the clinical study report will be based on the content of this statistical analysis plan (SAP). Details of the tables, listings, and figures to be prepared for the final CSR will be included in a study-specific Data Presentation Plan (DPP).

9.2 Other Reports and Reviews

The Scientific Steering Committee will closely review the safety data throughout the study to evaluate the overall risk/benefit profile as well as within the ECOG PS2 subgroup.

9.2.1 Safety Reviews

Safety reviews will begin when the following milestones have been met on the study:

- Ten patients in the ECOG PS2 subgroup have been dosed with at least 6 weeks of combination regimen therapy.
- Ten patients overall have been dosed with at least 12 weeks of combination therapy.

Once the initial safety review is concluded, the Scientific Steering Committee will conduct further reviews according to the previous results every 12 weeks. Safety reviews will include the following summaries:

- Subject disposition
- Demographics and other baseline characteristics
- Physical measurements and baseline disease characteristics

- AEs with focus on:
 - a) All or drug-related AEs
 - b) Immune-mediated, select AEs: incidence of all or drug-related event, time to onset and time to resolution
 - c) AEs leading to discontinuation of treatment
 - d) SAEs
- Subject death
- ECOG performance status over time
- Concomitant medication for drug-related selected AEs
- Time on study
- Doses and duration of study therapy

[REDACTED]

[REDACTED]

10 DOCUMENT HISTORY

Version Number	[REDACTED]	Date of Changes	Description
1.0	[REDACTED]	25Jan2018	Final version for approval
2.0	[REDACTED]	28Jan2019	Update per revised protocol v6.0

Version Number		Date of Changes	Description
2.1		27Jan2020	Deleted the subgroup analysis related to Weight base vs flat dose, and Non-Brain Metastatic column.
2.1		31Jan2020	The subgroups of weight-based vs. flat dose, and non-brain metastatic are removed from analyses, as they are not specified in the protocol.
2.1		23Feb2020	1)Corrected dates of change above.

APPENDIX 1 SELECT ADVERSE EVENTS DEFINITION AND CONVENTIONS

The select Adverse Events (select AEs) consist of a list of preferred terms grouped by specific category (e.g. pulmonary events, gastrointestinal events categories) and by subcategory (e.g. thyroid disorders, diabetes, pituitary, adrenal disorders subcategories). These categories and subcategories are defined by the Sponsor and the list that is most current at the time of analysis will be used. Also, changes may be made to this list with each new version of MedDRA.

For information, the select adverse events defined at the time of finalization of the first version of the document are listed in Table A-2 using MedDRA version 20.1. The final list used for the clinical study report will be included in an Appendix of the CSR.

Time-to onset definition

Time-to onset of select AE (any grade) for a specific category (i.e. pulmonary events, gastrointestinal events, ...) is defined as the time between the day of the first dose of study treatment and the onset date of the earliest select AE (of any grade) in this category.

If the subject did not experience a select AE (of any grade) in the category, time-to onset will be censored at the maximum follow-up time of all subjects in their respective treatment group (i.e. for subjects without an event, follow-up time is defined from first dosing date up to last dosing date +30 days (or 100 days depending on the analysis) if subjects are off treatment and followed for at least 30 days (or 100 days depending on the analysis) , otherwise it is defined up to the last known alive date). The resulting Kaplan-Meier plot will represent the cumulative rate of the select AE (any grade) in the category over time.

Time-to onset of select AE (grade 3-5) for a specific category is defined similarly but restricted to grade 3-5 select AEs.

Time-to onset of drug-related (grade 3-5 or any grade) select AE for a specific category is defined similarly but restricted to drug-related select AEs.

Time-to onset for a specific subcategory is defined similarly but restricted to event of this subcategory.

Time-to resolution definition

In order to derive the time-to resolution, overlapping or contiguous select AEs within a specific category (defined in Table A-2) will be collapsed into what will be termed “clustered” select AEs. For example, if a subject (without pre-treatment AE) experienced an AE from 1st to 5th January, another AE (with different PT but within same category) from 6th to 11th January and same AE from 10th to 12th January, these will be collapsed into one clustered select AE from 1st to 12th January. Table A-1 is summarizing key derivation steps for each type of clustered select AEs.

Time-to resolution of select AE (any grade) for a specific category is defined as the longest time from onset to complete resolution or improvement to the grade at baseline among all clustered select AEs in this category experienced by the subject. Events which worsened into grade 5

events (death) or have a resolution date equal to the date of death are considered unresolved. If a clustered select AE is considered as unresolved, the resolution date will be censored to the last known date alive. Improvement to the grade at baseline implies that all different AE events in the clustered select adverse event should at least have improved to the corresponding (i.e. with same preferred term) baseline grade. This measure is defined only for subjects who experienced at least one select AE in the specific category.

The time-to resolution of select AE (grade 3-5) for a specific category is defined similarly with an onset date corresponding to a grade 3-5 select AE.

Time-to resolution of drug-related select AE (any grade or grade 3-5) is defined similarly but restricted to drug-related select AE.

The time-to resolution of select AE (any grade or grade 3-5, drug-related or all) where immune modulating medication was initiated is defined similarly with the additional condition that the subject started an immune modulating medication during the longest select AE resolution period.

Time-to resolution for a specific subcategory is defined similarly but restricted to event of this subcategory.

Table A-1: Derivation of clustered select AE

Type of clustered select AE	Derivation
Any grade	Collapse any on-treatment select AE from the same category
Drug-related of any grade	Collapse any on-treatment drug-related select AE from the same category
Grade 3-5	Collapse any on-treatment select AE from the same category. Resolution will be based on the onset date of the earliest grade 3-5 records (if no grade 3-5 record, clustered select AE is excluded)
Drug-related of Grade 3-5	Collapse any on-treatment drug-related select AE from the same category Resolution will be based on the onset date of the earliest grade 3-5 record (if no Grade 3-5 record, clustered select AE is excluded)

The algorithm for collapsing select adverse event records is using the following conventions:

For each subject and specified category, the corresponding adverse event records will be collapsed when:

- 1) Multiple adverse event records have the same onset date.
- 2) The onset date of an event record is either the same day or 1 day later than the resolution date of a preceding event record (contiguous events).
- 3) The onset date of an event record is after the onset date and prior to or on the resolution date of a preceding event record (overlapping events).

Table A-2: Select Adverse Events

Category	Subcategory	Preferred Terms	
ENDOCRINE ADVERSE EVENT	ADRENAL DISORDER	ADRENAL INSUFFICIENCY	
		ADRENAL SUPPRESSION	
		ADRENOCORTICAL INSUFFICIENCY ACUTE	
		BLOOD CORTICOTROPHIN DECREASED	
		BLOOD CORTICOTROPHIN INCREASED	
		HYPOTHALAMIC PITUITARY ADRENAL AXIS SUPPRESSION	
		PRIMARY ADRENAL INSUFFICIENCY	
		SECONDARY ADRENOCORTICAL INSUFFICIENCY	
		DIABETES	DIABETES MELLITUS
			DIABETIC KETOACIDOSIS
	FULMINANT TYPE 1 DIABETES MELLITUS		
	LATENT AUTOIMMUNE DIABETES IN ADULTS		
	TYPE 1 DIABETES MELLITUS		
	PITUITARY DISORDER		HYPOPHYSITIS
		HYPOPITUITARISM	
		LYMPHOCYTIC HYPOPHYSITIS	
		THYROID DISORDER	ATROPHIC THYROIDITIS
	AUTOIMMUNE HYPOTHYROIDISM		
	AUTOIMMUNE THYROIDITIS		
	BASEDOW'S DISEASE		
	BLOOD THYROID STIMULATING HORMONE DECREASED		
	BLOOD THYROID STIMULATING HORMONE INCREASED		
	HYPERTHYROIDISM		
	HYPOTHYROIDISM		
	PRIMARY HYPERTHYROIDISM		
	PRIMARY HYPOTHYROIDISM		
	SILENT THYROIDITIS		
	THYROID FUNCTION TEST ABNORMAL		
	THYROID HORMONES DECREASED		
	THYROID HORMONES INCREASED		
	THYROIDITIS		
	THYROIDITIS ACUTE		
THYROXINE DECREASED			
THYROXINE FREE DECREASED			
THYROXINE FREE INCREASED			
THYROXINE INCREASED			
TRI-IODOTHYRONINE UPTAKE INCREASED			
GASTROINTESTINAL ADVERSE EVENT		AUTOIMMUNE COLITIS COLITIS	

Table A-2: Select Adverse Events

Category	Subcategory	Preferred Terms
		COLITIS ULCERATIVE DIARRHOEA ENTERITIS ENTEROCOLITIS FREQUENT BOWEL MOVEMENTS GASTROINTESTINAL PERFORATION LOWER GASTROINTESTINAL PERFORATION UPPER GASTROINTESTINAL PERFORATION
HEPATIC ADVERSE EVENT		ACUTE HEPATIC FAILURE ACUTE ON CHRONIC LIVER FAILURE ALANINE AMINOTRANSFERASE INCREASED ASPARTATE AMINOTRANSFERASE INCREASED AUTOIMMUNE HEPATITIS BILIRUBIN CONJUGATED INCREASED BLOOD ALKALINE PHOSPHATASE INCREASED BLOOD BILIRUBIN INCREASED DRUG-INDUCED LIVER INJURY GAMMA-GLUTAMYLTRANSFERASE INCREASED HEPATIC ENZYME INCREASED HEPATIC FAILURE HEPATITIS HEPATITIS ACUTE HEPATOTOXICITY HYPERBILIRUBINAEMIA LIVER DISORDER LIVER FUNCTION TEST ABNORMAL LIVER FUNCTION TEST INCREASED LIVER INJURY TRANSAMINASES INCREASED
HYPERSENSITIVITY/INFUSION REACTION		ANAPHYLACTIC REACTION ANAPHYLACTIC SHOCK BRONCHOSPASM HYPERSENSITIVITY INFUSION RELATED REACTION
PULMONARY ADVERSE EVENT		ACUTE RESPIRATORY DISTRESS SYNDROME ACUTE RESPIRATORY FAILURE IDIOPATHIC INTERSTITIAL PNEUMONIA INTERSTITIAL LUNG DISEASE LUNG INFILTRATION

Table A-2: Select Adverse Events

Category	Subcategory	Preferred Terms
RENAL ADVERSE EVENT		PNEUMONITIS
		ACUTE KIDNEY INJURY
		AUTOIMMUNE NEPHRITIS
		BLOOD CREATININE INCREASED
		BLOOD UREA INCREASED
		CREATININE RENAL CLEARANCE DECREASED
		HYPERCREATININAEMIA
		NEPHRITIS
		NEPHRITIS ALLERGIC
		PARANEOPLASTIC GLOMERULONEPHRITIS
		RENAL FAILURE
		RENAL TUBULAR NECROSIS
SKIN ADVERSE EVENT		TUBULOINTERSTITIAL NEPHRITIS
		URINE OUTPUT DECREASED
		AUTOIMMUNE DERMATITIS
		BLISTER
		DERMATITIS
		DERMATITIS ALLERGIC
		DERMATITIS EXFOLIATIVE
		DRUG ERUPTION
		ECZEMA
		ERYTHEMA
		ERYTHEMA MULTIFORME
		EXFOLIATIVE RASH
		FIXED DRUG ERUPTION
		NODULAR RASH
		PALMAR-PLANTAR ERYTHRODYSAESTHESIA SYNDROME
		PEMPHIGOID
		PHOTOSENSITIVITY REACTION
		PRURITUS
		PRURITUS ALLERGIC
		PRURITUS GENERALISED
	PSORIASIS	
	RASH	
	RASH ERYTHEMATOUS	
	RASH GENERALISED	
	RASH MACULAR	
	RASH MACULO-PAPULAR	
	RASH MORBILLIFORM	

Table A-2: Select Adverse Events

Category	Subcategory	Preferred Terms
		RASH PAPULAR RASH PRURITIC RASH VESICULAR SKIN EXFOLIATION SKIN HYPOPIGMENTATION SKIN IRRITATION STEVENS-JOHNSON SYNDROME TOXIC EPIDERMAL NECROLYSIS TOXIC SKIN ERUPTION URTICARIA VITILIGO

Source: MedDRA version 20.1
